Official Title: Foot progression angle modification: an exploratory six-week intervention in people with knee osteoarthritis.

NCT Number: TBD

Document Date: March 24th, 2020

Study Protocol

Study Design

This parallel-group randomized clinical trial will consist of a 6-week gait modification intervention, delivered to two groups of older adults with medial compartment knee osteoarthritis (OA). The first group will receive a conventional delivery of gait modification (group name: SMOD), whereby they will practice the gait modification with a specific target (rotate foot 15° inward or outward relative to baseline). The second group will self-select the amount of modification they perform (group name: AMAC), guided by the instruction to “change foot rotation as much as is comfortable”. Foot rotation (toe-in or toe-out walking) is measured during the stance phase of walking as the angle of the foot’s long axis (heel to toe) relative to the direction of walking, and termed foot progression angle (FPA). In-lab and real-world gait analysis will be used to examine how the modification is learned, as well as the effect of the modification on biomechanical and clinical outcomes relevant to knee OA. In-lab assessment will be performed at baseline and a 7 week follow-up, while real-world assessment will be performed during the intervening weeks using wearable sensor technology (a custom sensorized shoe design). Both within-group and between-group comparisons will be made to identify differences in learning, difficulty, biomechanical, and clinical outcomes.

Primary Hypotheses

- H1: Participants receiving the specific FPA target will exhibit improved learning outcomes (e.g. lower error in performance, higher proportion of steps with $\geq 7^\circ$ of change from baseline FPA and lower variability) from week 1 to week 6, as measured during gait modification practice sessions, learning assessments, and during daily walking activity.
- H2: Participants receiving the self-directed FPA modification will exhibit improved learning outcomes (higher proportion of steps with $\geq 7^\circ$ of change from baseline FPA and lower variability) from week 1 to week 6, as measured during gait modification practice sessions, learning assessments, and during daily walking activity.
- H3: We expect FPA variability will be larger in the self-directed group, but both groups will exhibit a similar proportion of steps with $> 7^\circ$ of change from baseline FPA.

Secondary Hypotheses

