A total of 36 individuals will be recruited for this study, 18 in each group. Approximately 60% in each group will be female. The primary outcome measure of this study is the change in absolute FPA performance error (the difference between the performed and the targeted FPA), which is indicative of how ‘accurate’ the patient is when performing the modification. This outcome measure is only relevant to the SMOD group, who have a specific target for their modification; therefore, allowing an error value to be calculated. This outcome will be measured during immediate and delayed retention at week one compared to follow-up and will provide evidence of the extent to which motor learning has occurred. Previous FPA performance error during immediate retention testing after a six-week FPA modification resulted in a small effect (Cohens $d = 0.35$) [3]. We are also interested in exploring the clinical and biomechanical differences between the SMOD and AMAC gait modification groups; however, no study has previously compared these methods of gait modification. Therefore, we will be conservative and base our sample size calculation on the between-within interaction effect of a 2×4 (group = 2: SMOD vs AMAC; measure = 4: immediate and delayed retention tests at week 1 and follow up) repeated measures ANOVA with an effect size of $f = 0.175$ ($f = d / 2$). With power = 0.8 and alpha = 0.05, a total sample of 30 is required [4]. With a conservatively estimated attrition of 15%, we will recruit 36 participants total (18 per group).

Procedures

Recruitment and screening

Volunteers will be recruited via print and social media, and via our database of previous participants who have indicated interest in participating in future studies. Interested volunteers will be screened via phone, email, or our lab website by the study coordinator to assess inclusion and exclusion criteria. Those deemed preliminarily eligible will be invited to attend a gait screening appointment. Eligible participants who pass the gait screen will be referred for a radiographic assessment of their knees to confirm the presence of structural signs of knee OA.

Standing, semi-flexed posteroanterior radiographs of both knees will be taken. A trained assessor will grade all radiographs based on the KL criteria. Those passing all screening requirements will be invited to enroll in the study.

Gait screening

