directly in front of the treadmill. The SMOD group will be guided to increase their FPA by 15° in either the toe-in or toe-out direction (determined by the gait screen). A line of tape will be aligned on the mirror according to the target FPA, as we have done previously [5, 17]. This mirror-based method of providing a target for the FPA modification was shown to be similarly effective when compared to feedback delivered using an expensive real-time motion capture system, but with significantly greater clinical feasibility. The AMAC group will be instructed to increase their FPA by “as much as is comfortable”. The mirror will be provided during practice sessions; however, no tapeline will be placed. The amount of time spent with the feedback (mirror) visible will be progressively reduced (faded feedback) across the six weekly practice sessions in order to reduce the reliance on feedback [18]. Before and immediately after the practice sessions, the participant will perform a warm-up and cool-down walk while wearing the sensorized shoes (10-minute outdoor standardized walking loop). This will provide a repeatable non-laboratory-based measure of FPA. Both groups will be encouraged to practice their gait modification at any opportunity during their daily at-home walking. Practice sessions will be led by a kinesiologist with experience delivering gait modification interventions.

Learning will be measured during 1) practice, 2) immediate and delayed retention tests, 3) dual-task tests, 4) transfer tests, and 5) during at-home/community walking. Each test (2-4) will last 1 min and be collected at each practice session. For the SMOD group, the absolute performance error (absolute error = |performed FPA – target FPA|), FPA variability, and the proportion of steps with >7° of change from baseline FPA will be measured using the sensorized shoe. For the AMAC group, FPA variability and the proportion of steps with >7° of change from baseline FPA will be measured. Retention tests will occur immediately before (starting at practice session 2) and after practice bouts. The participant will be asked to perform their gait modification as accurately as possible for 1 minute. Dual-task testing will be performed identically to the baseline assessment described above; however, the participant will be asked to simultaneously perform their gait modification. Lastly, transfer testing will be performed during stair ascent and descent in the same manner as the baseline assessment.

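### The 80% power belongs to a SMOD-versus-AMAC interaction that cannot be formed for the SMOD-only primary outcome, and the within-SMOD test has no stated power or precision

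*Protocol*

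**What the plan says.** The sample-size paragraph of the Protocol (Participants) declares change in absolute FPA performance error as the primary outcome and limits it to one arm: "This outcome measure is only relevant to the SMOD group, who have a specific target for their modification". On timing it says "This outcome will be measured during immediate and delayed retention at week one compared to follow-up".

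The effect size comes from that same outcome: "Previous FPA performance error during immediate retention testing after a six-week FPA modification resulted in a small effect", with d = 0.35. The paragraph then mentions interest in comparing the groups and the lack of earlier comparative data, and continues: "Therefore, we will be conservative and base our sample size calculation on the between-within interaction effect of a" 2×4 repeated measures ANOVA (two groups; immediate and delayed retention at week 1 and at follow-up), with f = d/2 = 0.175. The result: "With power = 0.8 and alpha = 0.05, a total sample of 30 is required". Attrition of 15% takes this to 36, or 18 per group.

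The section Gait modification intervention lists absolute error among the SMOD measures. The AMAC list opens "For the AMAC group, FPA variability and the proportion of steps with" more than 7° of change, and error is not on it.

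The SAP (Primary Hypotheses) plans repeated measures ANOVAs within each group and a two-way mixed ANOVA between groups. The mixed ANOVA analyses FPA change from baseline, not error.

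**The concern.** Three things that should refer to one variable and one test do not. The primary outcome is error in SMOD. The powered test compares SMOD with AMAC. The effect size behind that test comes from error, which AMAC does not have, while the planned mixed ANOVA uses another variable.

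A reader who meets the primary outcome, its effect size and the 80% figure in one paragraph will naturally attach the 80% to the primary outcome. It does not belong there. The test that does address the primary outcome rests on 18 recruited participants, about 15 after attrition, and nothing says what change it can detect or how precisely it will estimate one. Calling the interaction basis conservative strengthens the impression that the primary outcome is covered.

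**Working it through.** **Inputs.** From the Protocol: d = 0.35, f = 0.175, alpha 0.05, power 0.80, N = 30, four measures, 15% attrition, 18 per group. Not stated, so assumed: equal variances and equal correlations ρ among measures (which imply sphericity, ε = 1); d in single-test SD units; two-sided t tests. SMOD completers: 30/2 = 15 as planned, 18 with no loss.

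**1. The plan's own figure.** For the interaction, λ = N·4·f²·ε/(1 − ρ), with 3ε and 3ε(N − 2) degrees of freedom. With N = 30 and ε = 1, N·4·f² = 30 × 4 × 0.030625 = 3.675.

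- ρ = 0.50: λ = 7.35, power 59% (N = 46 would be needed for 80%).
- ρ = 0.68: λ = 11.48, power 80%.
- ρ = 0.70: λ = 12.25, power 83% (N = 28 falls just short of 80%).

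So 30 is the smallest even N for ρ of about 0.68–0.70. The attrition step is right: 30/0.85 = 35.3, and 36 gives equal groups.

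**2. What f = 0.175 means for the interaction.** Suppose the groups are equal at week 1 and differ by D (in SD units) at both follow-up retention tests. Each of the eight cells then has an interaction effect of ±D/4, so f = D/4 and D = 4 × 0.175 = 0.70 SD. That is twice the cited d. If D were 0.35, f would be 0.0875, and power at N = 30 would be 17% at ρ = 0.50 and 27% at ρ = 0.70. The conversion f = d/2 does fit a within-group change: means of 0, 0, d, d have deviations of ±d/2.

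**3. SMOD-only tests at the correlation that yields N = 30.**

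- Four-measure ANOVA: λ = n·4·f²/(1 − ρ), df 3 and 3(n − 1). For n = 15, 1.8375/0.32 = 5.74 and 1.8375/0.30 = 6.13. For n = 18, 2.205/0.32 = 6.89 and 2.205/0.30 = 7.35.
- One paired test, week 1 versus follow-up: standardised change d/√(2(1 − ρ)) = 0.35/√0.64 = 0.44 to 0.35/√0.60 = 0.45.
- Two retention tests averaged at each time: d/√(1 − ρ) = 0.35/√0.32 = 0.62 to 0.35/√0.30 = 0.64.

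| Within-SMOD test | Power, 15 completers | Power, 18 completers |
|---|---|---|
| Four-measure ANOVA | 46–49% | 55–58% |
| One paired test | 35–37% | 42–44% |
| Averaged contrast | 61–63% | 70–72% |

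The four-measure ANOVA would need 29–30 SMOD completers for 80%. The averaged contrast reaches about 80% at ρ = 0.80 with 15 completers, or ρ = 0.75 with 18. If the cited d is already in units of the SD of change, the paired test has 24% / 29%.

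**4. Precision of a single contrast, for which no ρ is needed.** The 95% CI half-width is t(0.975, n − 1)/√n: 2.145/√15 = 0.55 and 2.110/√18 = 0.50 SD of change. The change detectable with 80% power is 0.78 and 0.70 SD of change.

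**The case against.** The title calls the trial exploratory. The sample-size paragraph says openly that the primary outcome exists in SMOD only, that N rests on the interaction, and why; it never states that the 80% applies to error. The interaction can be formed for measures both groups share, and one primary hypothesis, H3, is between-group: "We expect FPA variability will be larger in the self-directed group, but both groups will exhibit a similar proportion of steps with" more than 7° of change. All of this stands, and it lowers the severity. It does not supply the missing precision, nor explain why an effect on error should describe a group difference in another variable.

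Three stronger readings are tempting, and the documents do not support them.

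- **That N = 30 is miscalculated.** It is attainable at ρ of about 0.68–0.70. What is missing is the assumption, not the arithmetic.
- **That the primary outcome's measures are undefined.** The sample-size paragraph names the retention tests at week 1 and follow-up. H1 speaks of change "from week 1 to week 6, as measured during gait modification practice sessions, learning assessments" and daily walking, and the SAP of the whole six weeks, but both cover a family of learning outcomes and do not displace the specific definition. What is not stated is which single contrast of those tests is primary.
- **That a null result could not be interpreted.** An estimate with its confidence interval can be read without a prior power figure.

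The 0.70 SD equivalence depends on the pattern assumed in step 2, and conservative may have meant applying a small effect to the more demanding between-group question. The plan should then say so.

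**Conclusion.** The concern holds as a mismatch between the primary outcome and the powered test. That part needs no calculation: there are no AMAC error values, so the stated 80% cannot refer to the declared primary outcome, and no other power or precision is given for it.

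Its size depends on assumptions the documents do not state. With equal correlations of 0.68–0.70, the values that reproduce N = 30, power for the primary outcome runs from 35% to 63% with 15 completers and from 42% to 72% with 18, depending on the test. A reader might infer that the primary outcome is certainly underpowered. That does not follow: a higher correlation together with the averaged contrast could reach 80%. The conclusion is that adequacy turns on a test and a correlation that are not specified. Should be fixed; it does not put the trial in question.

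**What to change.** Keep 36 participants.

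1. In the sample-size paragraph, state that the 80% applies to the group-by-measure interaction and not to the primary outcome. Tie it to an outcome both groups have, and give the assumed ρ and ε. State that f = 0.175 is a between-group difference in change of about 0.70 SD if the difference appears equally at both follow-up retention tests. Then either justify the word conservative or remove it.
2. Name one within-SMOD primary contrast, for example week 1 versus follow-up with the two retention tests averaged at each time, and carry it into the SAP. Two places must be reconciled first. Gait modification intervention starts the pre-practice retention tests at session 2, so delayed retention at week 1 needs a definition. Baseline and follow-up data collection lists no retention test at follow-up.
3. Give that contrast's precision: detectable change at 80% power of about 0.78 SD of change with 15 completers and 0.70 with 18; 95% CI half-width of about 0.55 and 0.50. Commit to reporting the primary outcome with its 95% CI.

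The cost is rewording one Protocol paragraph and one SAP sentence, plus settling when the retention tests take place. No extra participants are needed. The drawback is that the stated power will look less favourable.

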- H4: Those in the self-directed modification group will exhibit smaller average changes in FPA compared to those in the conventional gait modification group. However, those in the self-directed modification group will report lower ratings of difficulty in performing the modification, compared to the specific-target gait modification group.
- H5: Both groups will exhibit improvements in biomechanical (e.g. knee adduction moment) and clinical outcomes (e.g. knee pain, physical function) at follow-up, compared to baseline.
- H6: Biomechanical (e.g. knee adduction moment) and clinical outcome (e.g. knee pain, physical function) change scores from baseline to follow up will not differ between groups.

Participants

Adults with knee OA will be recruited and randomized into two treatment arms. All eligible

participants will: 1) be 50 years of age or greater, 2) exhibit signs of tibiofemoral OA (a score of ≥ 2 on the Kellgren and Lawrence (KL) grading scale [1]) predominantly in the medial compartment, 3) self-reported knee pain $\geq 3 / 10$ on a numerical rating scale of pain (NRS; 0 = “no pain” and 10 = “worst pain imaginable”) during most days of the previous month, 4) are comfortable walking intermittently for 30 minutes, and 5) fit into the available sizes of sensorized shoes (sizes spanning US women’s 5 to men’s 13).

Exclusion criteria include: 1) any knee surgery or intraarticular injections within the past 6 months, 2) a history of joint replacement surgery or high tibial osteotomy, 3) current or recent (within 6 weeks) corticosteroid injections, 4) use of a gait aid, 5) currently on a wait list for joint replacement surgery or high tibial osteotomy, 6) any inflammatory arthritic condition, 7) any other conditions that may affect normal gait or participation in an aerobic exercise program, and 8) cannot attend all required appointments at UBC. Additionally, potential participants will undergo an initial gait screening similar to a recent study [2] (details are outlined below), with the goal of identifying participants who are capable of reducing their KAM magnitude when FPA is modified. This gait screen will examine both natural walking FPA and changes in knee load while walking with increased toe-in and toe-out. Those who do not elicit a reduction in KAM impulse $\geq 5\%$ when FPA is changed by 10° in either direction will be excluded from the study as they would be considered non-responders.

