Stair ascent and descent will be performed while wearing the sensorized shoes. This will take place at a building nearby the laboratory (5-minute walk) because of the availability of continuous linear sets of stairs for multiple flights. This allows the use of the sensorized shoe for measuring FPA during stair ascent and descent. These FPA data will be compared with transfer test data (details included below) examined at several points throughout the intervention. These same shoes will be provided to the participant to measure real-world FPA during at-home and community walking.

Sensorized shoes

A custom inertial sensor consisting of a 3-axis accelerometer (signal range: $\pm 4g$), gyroscope ($\pm 500^\circ/s$), and magnetometer ($\pm 1200\mu T$), sampling data at 100 Hz will be embedded in the sole of the shoe. A previously published custom sensor fusion algorithm [13], programmed into a microcontroller, calculates the FPA in real time and stores it on a microSD card for later extraction. The sensorized shoe design and algorithm has been validated during treadmill [14] and over-ground walking [15] with excellent validity and reliability (absolute error = 1.7° and intraclass correlation coefficients > 0.9).

Randomization

Once deemed eligible and baseline data collection is complete, each participant will be randomized to either the SMOD or AMAC group. Randomization will be performed using an *a priori* block-stratified approach based on sex and KL grade. A predetermined randomization matrix will be computed [16] by a team member not involved in testing or the intervention. Group allocations will be stored in opaque envelopes, which will be opened in a sequential manner after baseline testing and before the first practice session. The group allocation will be communicated to the study trainer via email.

Gait modification intervention

Both groups will attend six practice sessions conducted weekly, which will last approximately 1 hour each. Walking practice will be conducted on a treadmill with a full-length mirror placed

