Official Title: Foot progression angle modification: an exploratory six-week intervention in people with knee osteoarthritis.

NCT Number: TBD

Document Date: Mar 24th, 2020

Statistical Analysis Plan

Statistical analyses will be performed by an independent statistician. Means and standard deviations will be calculated for each outcome measure and baseline demographic characteristic. Baseline demographic data (e.g. age, body mass index, disease severity) will be examined for between-group differences using unpaired two-tailed t-tests. For all statistical analyses, alpha will be set to 0.05. Any multiple pairwise comparisons will be adjusted using the Bonferroni correction method.

Data will be assessed for sphericity, homoscedasticity, and normality using Mauchley's test, residual versus predicted plots, and quantile-quantile plots. Homoscedasticity and normality assumptions will be confirmed using Levene's test and Shapiro-Wilk's test, respectively. Sphericity assumption violations will be corrected for using the Greenhouse Geisser approach. Violations of homoscedasticity will be corrected for by bootstrapped model parameters. If normality is not met, a non-parametric test will be used.

Primary Hypotheses:

Repeated measures analyses of variance (ANOVA) will be performed to examine the within-group changes in learning outcomes over the six-week intervention. Between-group differences will be examined using a two-way mixed ANOVA, with the repeated measure being the learning outcome (foot progression angle change from baseline during in-lab and at-home walking) and the between-subject factor being group assignment (SMOD vs AMAC).

Secondary Hypotheses:

Biomechanical (knee joint moments), clinical (NRS knee pain, KOOS pain, symptoms, and physical function scores), and difficulty (difficulty of performing the FPA modification) change scores will be examined using an analysis of covariance (ANCOVA) with significant between-group baseline demographic group differences and baseline outcome values included as covariates.

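### The 80% power belongs to the group-by-measure interaction over four post-allocation tests. It does not cover the level differences predicted in H3 (variability) and H4 (FPA change), and the choice is not conservative.

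*Protocol*

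**What the plan says.** **Sample size (Protocol, Participants).** The protocol notes that no earlier study has compared the two delivery methods and gives this as the reason for its choice: "we will be conservative and base our sample size calculation on the between-within interaction effect of a 2×4" repeated measures ANOVA. The layout is "group = 2: SMOD vs AMAC; measure = 4: immediate and delayed retention tests at week 1 and follow up". The effect size is f = d/2 = 0.175, from d = 0.35. With alpha 0.05 and power 0.8 the total is 30, raised to 36 for 15% attrition. No correlation among the repeated measures is given.

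**Timing (Protocol, Randomization and Gait modification intervention).** Allocation envelopes are "opened in a sequential manner after baseline testing and before the first practice session". Retention tests follow each practice bout; from session 2 there is also one before practice.

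**Hypotheses.** H3, listed as primary, says "We expect FPA variability will be larger in the self-directed group", and adds that the proportion of steps beyond 7° will be similar. H4, listed as secondary, says "Those in the self-directed modification group will exhibit smaller average changes in FPA compared to those in the conventional gait modification group", and adds that AMAC will find the modification less difficult.

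**Analysis (SAP, Primary Hypotheses).** "Between-group differences will be examined using a two-way mixed ANOVA", with group as the between-subject factor. The SAP does not say which term of that model is the test.

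**The concern.** In a pre/post trial the group-by-time interaction is the treatment effect, because the first measure precedes treatment and the arms start level. That does not hold here. The earliest retention test already follows practice under the allocated instruction, either a 15° target or as much change as is comfortable. The interaction null is therefore parallel profiles: the same gap between arms at all four tests. Any part of the gap that is common to the four tests drops out of the interaction.

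The variability part of H3 and the FPA part of H4 are about that common part. A reader who takes 80% as the trial's power to compare the arms would be misled about both. A non-significant interaction could also be reported as no difference between the arms when the average level does differ.

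**Working it through.** **Inputs.** From the Protocol: k = 2 groups, m = 4 measures, f = 0.175, alpha 0.05, power 0.80, N = 30 completers, N = 36 recruited, 1:1 allocation. Assumed, because not stated: a common correlation ρ between measures (range 0.3 to 0.9) and no sphericity correction. SD means the between-person SD at a single test.

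**Step 1. Reproduce N = 30 (interaction).** Noncentral F with λ = f²Nm/(1 − ρ) and df = (m − 1), (N − 2)(m − 1) = 3, 84.
- ρ = 0.50: λ = 0.030625 × 30 × 4 / 0.50 = 7.35; power 59%; N needed 46.
- ρ = 0.68: λ = 3.675 / 0.32 = 11.48; power 80.2%; N needed 30.

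The stated 30 is obtained for ρ of about 0.68 to 0.70. The attrition step reproduces: 30/0.85 = 35.3, so 36.

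**Step 2. Same f, group effect (mean level over the four tests).** λ = f²Nm/(1 + (m − 1)ρ), df = 1, N − 2. At ρ = 0.68 the divisor is 1 + 3 × 0.68 = 3.04.
- N = 30: λ = 3.675 / 3.04 = 1.21; power 19%.
- N = 36: λ = 4.41 / 3.04 = 1.45; power 22%.

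| Assumed ρ | Group-effect power, N = 30 | Group-effect power, N = 36 | N for 80%, group effect | N for 80%, interaction | Level difference detectable at 80%, N = 30 |
|---|---|---|---|---|---|
| 0.3 | 27% | 32% | 124 | 64 | 0.73 SD |
| 0.5 | 22% | 25% | 164 | 46 | 0.84 SD |
| 0.68 | 19% | 22% | 198 | 30 | 0.92 SD |
| 0.9 | 16% | 19% | 240 | 12 | 1.02 SD |

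Across this range the interaction needs fewer participants than the group effect. The order reverses at ρ = 0 (92 against 68), but ρ = 0 cannot be what lies behind a stated total of 30.

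**Step 3. How the two terms behave (15 per arm, ρ = 0.68).**
- *Constant gap of 1.0 SD.* The interaction noncentrality is zero, so it rejects at 5%. For the group effect, f = 0.5 and λ = 0.25 × 30 × 4 / 3.04 = 9.87, so power is 86%. A simulation of 8,000 runs gave 5.0% and 85.3%.
- *Gap that opens with training: 0, 0, 0.7, 0.7 SD.* The mean gap is 0.35 SD, and the departures from it are ±0.35 SD. Both terms then have f = 0.175, and Steps 1 and 2 apply: interaction 80%, group effect 19%. At ρ = 0.5 the figures are 59% and 22%.

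Neither term stands in for the other. Which has more power depends on the shape of the gap, and the documents do not predict that shape.

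**The case against.** **The SAP does not adopt the interaction as the test.** This stands. Only the sample size rests on that term. The mixed ANOVA also yields a group effect, and the SAP names group as the between-subject factor. A reader might infer that H3 and H4 will be judged on the interaction, so that a true steady difference would be missed about 95% of the time. The documents do not say so; the SAP leaves the term open.

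**The gap need not be steady.** This stands too. One might read H3 and H4 as predicting a constant difference from the first session. They give no timing. H1 and H2 expect change from week 1 to week 6, and feedback is faded over the sessions. The study design also aims to identify between-group differences in learning, and the interaction answers that aim. With the growing gap in Step 3 it is the more powerful term, so it should not be discarded.

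**Power for H3 and H4 is never expressly claimed, and the title calls the study exploratory.** True. But H3 is a primary hypothesis, and the exploring language in the sample-size paragraph concerns clinical and biomechanical differences. That paragraph gives its interest in comparing the arms as the reason for the interaction-based size, which invites a reader to take 80% as between-arm power.

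**The 19% borrows an f that is not a between-arm contrast.** Correct: d = 0.35 comes from FPA performance error after training in an earlier study. The 19% shows what the plan's own f implies for the other term; it is not a forecast. The detectable difference is the better figure to print.

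**Conclusion.** The point holds for the sample-size statement. The 80% is the power to detect a change in the between-arm gap across four post-allocation tests. It does not apply to H3 variability or H4 average FPA change. For a level difference of the same f, power is about 19% with 30 completers and 22% with 36, under equal correlations of about 0.68, a value back-solved from N = 30 and not stated in the protocol. Over correlations of 0.9 to 0.3 the figure at N = 30 is 16% to 27%, so the conclusion does not hang on that value. Calling the choice conservative is wrong, since at the plan's f and implied correlation the interaction needs 30 participants and the group effect 198.

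On the analysis, the finding is only that the SAP does not name the tested term. The point does not extend to two other parts of the hypotheses. H3's similar proportion of steps is a similarity claim, which a non-significant result on either term would not establish. H4's difficulty rating is assigned to ANCOVA.

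**What to change.** **Protocol, sample-size paragraph**
- Delete *conservative* as the description of choosing the interaction.
- State the repeated-measures correlation that was assumed.
- Say that the 80% refers only to a change in the between-arm gap across the four retention tests.
- Give the level difference detectable with 80% power at 30 completers: about 0.7 to 1.0 SD for correlations 0.3 to 0.9, or 0.92 SD at 0.68.
- Keep N = 36.

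**SAP, between-group analysis**
- State that H3 variability and H4 average FPA change are judged on the group effect, meaning the difference in mean level over the prespecified tests, with its 95% confidence interval.
- Report the group-by-measure interaction separately, as the test of whether learning differs between arms.
- State that a non-significant interaction will not be read as absence of a group difference.
- Do not apply this wording to H3's proportion of steps or H4's difficulty rating.

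**Cost.** Wording only, with no extra data or participants. The downside is that the stated power for between-arm comparisons becomes much less favourable.
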